5.0 Consent Process and Documentation

5.1 Consent Process

5.1.1 Obtaining Informed Consent

5.1.1.1 Timing and Location of Consent

Subjects presenting to the study investigator's practice site as part of their initial or routine evaluation will be given the opportunity to participate in the research study. Patients will be given information about the study and asked to participate. If eligible, based on inclusion and exclusion criteria, informed consent will be obtained at the time of the screening visit and the patient will be enrolled in the study.

5.1.1.2 Coercion or Undue Influence during Consent

Subjects will be given ample time to read and review the consent form on their own. All questions the patient may have will be answered and written consent will be obtained. A member of the research team will assist in the explanation and obtaining of the written consent. A copy of the signed consent will be given to the patient and another copy sent to Medical Records.

5.1.2 Waiver or alteration of the informed consent requirement – N/A

5.2 Consent Documentation

5.2.1 Written Documentation of Consent

A member of the research team will assist in the explanation and obtaining of the written consent. A copy of the signed consent will be given to the patient and another copy sent to Medical Records.

5.2.2 Waiver of Documentation of Consent – N/A

5.3 Consent – Other Considerations

5.3.1 Non-English Speaking Subjects – N/A

5.3.2 Cognitively Impaired Adults - N/A

5.3.2.1 Capability of Providing Consent - N/A

5.3.2.2 Adults Unable To Consent - - N/A

5.3.2.3 Assent - N/A

5.3.3 Subjects who are not yet adults (infants, children, teenagers)

5.3.3.1 Parental Permission - N/A

5.3.3.2 Assent – N/A

6.0 HIPAA Research Authorization and/or Waiver or Alteration of Authorization

6.1 Authorization and/or Waiver or Alteration of Authorization for the Uses and Disclosures of PHI

Check all that apply:

- Authorization will be obtained and documented as part of the consent process.
- Partial waiver is requested for recruitment purposes only (*Check this box if patients' medical records will be accessed to determine eligibility before consent/authorization has been obtained*)
- Full waiver is requested for entire research study (e.g., *medical record review studies*)
- Alteration is requested to waive requirement for written documentation of authorization

6.2 Waiver or Alteration of Authorization for the Uses and **Disclosures of PHI**

6.2.1 Access, use or disclosure of PHI representing no more than a minimal risk to the privacy of the individual

6.2.1.1 Plan to protect PHI from improper use or disclosure

Information is included in Section 10 of this protocol

6.2.1.2 Plan to destroy identifiers or a justification for retaining identifiers

The list will be destroyed upon completion of the study.

6.2.2 Explanation for why the research could not be practicably be conducted without access to and use of PHI

Patient identifiers are necessary for identification and review of the patient's medical records. A unique study code number will be used for identification of study data. The linking list will be destroyed upon completion of the study.

6.2.3 Explanation for why the research could not practicably be conducted without the waiver or alteration of authorization – N/A**6.3 Waiver or alteration of authorization statements of agreement**

Protected health information obtained as part of this research will not be reused or disclosed to any other person or entity, except as required by law, for authorized oversight of the research study, or for other permitted uses and disclosures according to federal regulations.

The research team will collect only information essential to the study and in accord with the 'Minimum Necessary' standard (information reasonably necessary to accomplish the objectives of the research) per federal regulations.

Access to the information will be limited, to the greatest extent possible, within the research team.

All disclosures or releases of identifiable information granted under this waiver will be accounted for and documented.

7.0 Study Design and Procedures

7.1 Study Design

This will be a prospective, randomized, double-blind study in which patient and data collector is blinded to the treatment protocol. The physician who is preparing and performing the injection will remain unblinded.

Recruitment → Randomization → Treatment (Corticosteroid v corticosteroid/lidocaine v corticosteroid/saline)

Corticosteroid (CS) → post-injection assessment immediately following injection → post-injection assessment at 6 weeks (via phone)

Corticosteroid/lidocaine (CSL) combination → post-injection assessment immediately following injection → post-injection assessment at 6 weeks (via phone)

Corticosteroid/saline (CSS) combination → post-injection assessment immediately following injection → post-injection assessment at 6 weeks (via phone)

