2.2 Previous Data

Previous studies have evaluated the efficacy of steroid injections as compared to placebo injections in the treatment of trigger finger but no previous studies have compared steroid/lidocaine injections to injections without lidocaine. The aim of this study is to compare post-injection pain and efficacy of trigger finger injection using a combination of lidocaine/corticosteroid versus corticosteroid injection alone or corticosteroid/saline (equal volume). Our hypothesis is that lidocaine causes unnecessary pain upon injection and does not improve the efficacy of the steroid in providing sustained anti-inflammatory benefit. We also seek to determine if volume of injection plays a role in immediate post-injection pain (corticosteroid/saline group).

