7.2 Study Procedures**7.2.1 Visit 1 – Screening/Baseline Visit**

Patients will be given information about the study and asked to participate. If eligible, based on inclusion and exclusion criteria, informed consent will be obtained at the time of the screening visit and the patient will be enrolled in the study.

After obtaining informed consent, the patient will be randomized to one of three treatment groups. The study investigator (who is unblinded) will randomly draw a sealed envelope

containing one of the three treatment groups. The sealed envelopes will be stored in a secure area within the clinic practice site.

- CS – corticosteroid alone -1 cc dexamethasone (4mg/ml) only
- CSL – corticosteroid/lidocaine combination - 1 cc dexamethasone (4mg/ml) and 1 cc 1% lidocaine
- CSS – corticosteroid/saline combination - 1 cc dexamethasone (4mg/ml) and 1 cc 0.9% injectable saline)

The patient will then be asked to complete a Patient Survey pre-injection (VAS Pain Scale and Trigger question). The study investigator will perform a single injection using a 25 gauge 1.5" needle. The needle will be inserted at 90 degrees to the skin, 1 cm proximal to the metacarpophalangeal joint flexion crease. The injections will be prepared in the Bone & Joint Institute as part of standard of care.

The patient will then complete the Patient Survey at 1 minute and 10 minutes following injection (VAS Pain Scale and Trigger question).

Objective hand exam will be performed including range of motion at MP, PIP and DIP joints, presence of clicking or locking, triggering score, pain with range of motion and grip strength as part of the patient's standard of care.

7.2.2 6-Week Follow-Up Phone Call

The patient will be contacted via phone and will be asked to verbally complete the Patient Survey (patient will be asked to report the VAS Pain score over the phone in .5 increments – i.e. 3.5, 4.0, 5.0, 5.5, etc.) and the coordinator will record the score. The patient will also answer question about how often he/she triggers (see phone script).

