7.4.5 Blinding of the Test Article

The three drug combinations will be compounded in the Bone & Joint Institute as part of routine standard of care.

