7.4.6.2 Preparation and Dispensing

Subject randomization will be performed prior to dispensing of any study drugs. After randomization, subjects will be dispensed study drugs as follows:

- CS – corticosteroid alone - 1 cc dexamethasone (4mg/ml) only
- CSL – corticosteroid/lidocaine combination - 1 cc dexamethasone (4mg/ml) and 1 cc 1% lidocaine
- CSS – corticosteroid/saline combination - 1 cc dexamethasone (4mg/ml) and 1 cc 0.9% injectable saline)

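### The unblinded injector's words, reassurance and pace are not standardised before the 1- and 10-minute pain scores; a fixed script and delivery procedure would narrow this bias route cheaply

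*Combined protocol and SAP*

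**What the plan says.** Section 7.1 describes a "double-blind study in which patient and data collector is blinded to the treatment protocol". It then makes an explicit exception: "The physician who is preparing and performing the injection will remain unblinded". The exception covers all three arms.

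Section 7.2.1 shows how the injector learns the arm: "The study investigator (who is unblinded) will randomly draw a sealed envelope". The same role then gives the injection. The text sets the needle gauge and length, the angle to the skin and the entry point, and 7.4.2 repeats these. Neither section covers the speed of injection, what the patient is told or what reassurance is given. The patient completes the survey, including the VAS, before the injection and again 1 and 10 minutes after it. The 6-week score is taken by telephone and recorded by the coordinator.

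Section 2.2 states the expected direction: "Our hypothesis is that lidocaine causes unnecessary pain upon injection". It also identifies the saline arm as the equal-volume comparator.

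Section 7.4.5, headed as blinding of the test article, describes no masking step. It says "The three drug combinations will be compounded in the Bone & Joint Institute as part of routine standard of care". Section 7.4.6.2 adds: "After randomization, subjects will be dispensed study drugs as follows". Neither names the person who prepares the syringe.

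**The concern.** Pain from an injection depends partly on how it is given and on what the patient is led to expect. Here both are left to a person who knows the allocation and works under a protocol with a stated expectation about one arm. The outcome most exposed is a self-rating made one minute later.

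The blinding in 7.1 protects how pain is rated and recorded. It does not protect how the injection is delivered. Hiding the syringe from the patient and data collector would leave the injector's own knowledge untouched.

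The contrast with most at stake is CSL v CSS, because it alone separates lidocaine from volume. Every injector knows the arm for every patient, so a difference in handling between arms would coincide with the drug difference. No analysis of the planned data could separate the two.

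**Working it through.** **1. Which contrast isolates lidocaine (volumes from 7.2.1).**
- CS: 1 cc dexamethasone = 1 cc.
- CSL: "corticosteroid/lidocaine combination - 1 cc dexamethasone (4mg/ml) and 1 cc 1% lidocaine" = 2 cc.
- CSS: 1 cc dexamethasone + 1 cc saline = 2 cc.

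CSL v CS changes lidocaine and volume together. CSS v CS changes volume only. CSL v CSS changes lidocaine only.

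**2. The plan's own sample size (9.1).** The inputs are a difference of 5 mm, SD 10 mm and 15% dropout; 9.2 gives two-sided 0.05. Power is not stated. Assuming 80%, the two-sample t-test needs 63.8, so 64 per arm. Then 3 × 64 = 192 and 192 × 1.15 = 220.8, so 221. Both planned figures reproduce, and this point does not dispute them.

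**3. Patients per arm for the sensitivity check.**
- Low end, full planned dropout: 221 × 0.85 / 3 = 62.6, about 63.
- High end: 74 per arm (16.0). This suits the 1- and 10-minute scores better, because they are taken at the injection visit, before most dropout can occur.

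**4. Standard error of a difference**, SE = 10 × √(2/n):
- n = 63: 10 × √(2/63) = 1.78 mm.
- n = 74: 10 × √(2/74) = 1.64 mm.

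**5. False-positive risk.** Assume that injector behaviour shifts the CSL − CSS mean by b mm and that there is no true difference. The rejection probability is that of a two-sided 0.05 t-test with 2n − 2 degrees of freedom and noncentrality b/SE.

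| Assumed shift b | n = 63: b/SE | n = 63: P(p<0.05) | n = 74: b/SE | n = 74: P(p<0.05) |
|---|---|---|---|---|
| 0 mm | 0 | 5.0% | 0 | 5.0% |
| 1 mm | 0.56 | 8.6% | 0.61 | 9.3% |
| 2 mm | 1.12 | 20.0% | 1.22 | 22.7% |
| 3 mm | 1.68 | 38.6% | 1.82 | 44.2% |

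**6. The opposite direction.** An injector who expects pain might reassure more or inject more gently in the lidocaine arm. If that offsets a true 5 mm difference by b, the noncentrality is (5 − b)/SE.

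| Assumed offset b | Power, n = 63 | Power, n = 74 |
|---|---|---|
| 0 mm | 80% | 86% |
| 1 mm | 61% | 68% |
| 2 mm | 39% | 44% |
| 3 mm | 20% | 23% |

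The shifts of 1 to 3 mm are assumptions. They are 20% to 60% of the 5 mm target (1/5 to 3/5), which is why modest differences in handling would matter.

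**The case against.** The strongest reply is that the plan discloses the unblinded injector and already protects the outcome. The patient rates the pain and is blinded, the data collector is blinded, and the 6-week score comes by telephone. Any bias must act indirectly, through words or technique, and nothing in the documents shows that it occurs. All of this stands. It makes the point a design weakness with a cheap remedy, not an error. It also confines the point mainly to immediate pain, although 1.2 makes efficacy primary as well.

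It is also fair that 7.1 already keeps the injector from being the data collector, since one is unblinded and the other blinded. But 7.1 does not stop the injector from staying in the room while the patient completes the surveys.

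Three stronger readings are tempting, and the documents do not support them:

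- *That 7.1 contradicts 7.4.5 to 7.4.6.2 on who prepares the injection.* Section 7.1 names the physician. The later sections, like 7.2.1, use the passive voice, give a place and name nobody else. The storage wording in 7.4.6.1 hints at advance preparation but also names no preparer. The text is ambiguous, and all of it is compatible with the physician preparing the syringe in the clinic.
- *That the injector could readily be blinded between CSL and CSS through an existing dispensing step.* Equal volume removes one obstacle. No section documents a separate preparer, and none says that the two mixtures look alike.
- *That each injector personally believes lidocaine hurts.* Section 2.2 records the protocol's hypothesis, not the belief of each physician.

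**Conclusion.** The point holds as a cheap improvement. The plan leaves the verbal and technical conduct of the injection to someone who knows the arm, immediately before a self-rated pain score, and blinding the patient and data collector does not close that route. The consequence is greatest for CSL v CSS at 1 and 10 minutes and smaller for the 6-week telephone score.

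The size and direction of any injector effect are unknown. Over an assumed range of 1 to 3 mm, the false-positive risk for this contrast would rise from 5% to between about 9% and 44%. An effect in the other direction would cut power for a true 5 mm difference to between about 68% and 20%. Both ranges rest on the plan's SD of 10 mm and on 63 to 74 patients per arm. They show how sensitive the contrast is; they do not show that a bias of this size will arise.

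**What to change.** Add to 7.2.1 that, in all three arms, the injector:

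1. uses one fixed, neutral script;
2. does not mention the contents of the syringe or the sensation to expect;
3. follows the same pre-specified delivery procedure, including pace, which the investigators are to set;
4. is neither present for nor involved in the 1- and 10-minute surveys.

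State in 7.4.5 to 7.4.6.2 who prepares the injection.

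A further step is worth considering only if a separate preparer already exists and the two 2 cc mixtures look alike. That person could open the envelope and hand over a syringe labelled with a code, with the allocation resealed and concealed. The envelope step in 7.2.1 and the unblinding entry in 21.6 (now not applicable) would then need matching revisions. CS would still be recognisable by its 1 cc volume.

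The main change costs some protocol wording, a short script and brief training. It needs no extra staff and leaves the arms, sample size and endpoints as they are. It should be in place before enrolment, because the analysis cannot repair the problem later. The downside is that the injector remains unblinded, so the risk is reduced, not removed.

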7.2 Study Procedures**7.2.1 Visit 1 – Screening/Baseline Visit**

Patients will be given information about the study and asked to participate. If eligible, based on inclusion and exclusion criteria, informed consent will be obtained at the time of the screening visit and the patient will be enrolled in the study.

After obtaining informed consent, the patient will be randomized to one of three treatment groups. The study investigator (who is unblinded) will randomly draw a sealed envelope

containing one of the three treatment groups. The sealed envelopes will be stored in a secure area within the clinic practice site.

- CS – corticosteroid alone -1 cc dexamethasone (4mg/ml) only
- CSL – corticosteroid/lidocaine combination - 1 cc dexamethasone (4mg/ml) and 1 cc 1% lidocaine
- CSS – corticosteroid/saline combination - 1 cc dexamethasone (4mg/ml) and 1 cc 0.9% injectable saline)

The patient will then be asked to complete a Patient Survey pre-injection (VAS Pain Scale and Trigger question). The study investigator will perform a single injection using a 25 gauge 1.5" needle. The needle will be inserted at 90 degrees to the skin, 1 cm proximal to the metacarpophalangeal joint flexion crease. The injections will be prepared in the Bone & Joint Institute as part of standard of care.

The patient will then complete the Patient Survey at 1 minute and 10 minutes following injection (VAS Pain Scale and Trigger question).

Objective hand exam will be performed including range of motion at MP, PIP and DIP joints, presence of clicking or locking, triggering score, pain with range of motion and grip strength as part of the patient's standard of care.

7.2.2 6-Week Follow-Up Phone Call

The patient will be contacted via phone and will be asked to verbally complete the Patient Survey (patient will be asked to report the VAS Pain score over the phone in .5 increments – i.e. 3.5, 4.0, 5.0, 5.5, etc.) and the coordinator will record the score. The patient will also answer question about how often he/she triggers (see phone script).

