4.0 Recruitment Methods

4.1 Identification/Recruitment of subjects

Subjects will be identified as part of their initial or routine evaluation by one of the study investigators in the Bone & Joint Institute.

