4.2 Recruitment materials – N/A

4.3 Eligibility/screening of subjects

Adult patients presenting to the Bone & Joint Institute will be evaluated as part of standard of care. Those subjects meeting eligibility requirements will be presented with the opportunity to participate in the research study by a member of the research team.

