7.4.3 Method for Assigning Subject to Treatment Groups

Patients will be randomized to receive CS, CSL, or CSS during their clinic visit.

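### The unblinded investigator who injects also draws the allocation from a pool of envelopes in clinic, and no stated step would prevent or reliably reveal a re-draw after opening

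*Combined protocol and SAP*

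**What the plan says.** Section 7.2.1 puts consent first: "After obtaining informed consent, the patient will be randomized to one of three treatment groups". It then gives the mechanism: "The study investigator (who is unblinded) will randomly draw a sealed envelope", and each envelope holds one of the three groups. On custody it says: "The sealed envelopes will be stored in a secure area within the clinic practice site". The same section has the study investigator give the injection, and section 7.1 confirms that "The physician who is preparing and performing the injection will remain unblinded".

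Section 7.4.3, which is headed as the method of assignment, says only: "Patients will be randomized to receive CS, CSL, or CSS during their clinic visit". Section 7.4.5, on blinding, says only that the combinations are compounded in the clinic. Section 22.1.1, on quality control, covers data storage and oversight by the principal investigator.

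The stated safeguards are therefore three: sealed envelopes, secure storage, and consent before the draw. The protocol does not mention a pre-generated sequence, numbered or opaque envelopes, an independent preparer or custodian, an entry made before opening, or a count of used and unused envelopes.

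**The concern.** The person who draws the envelope is the person who learns the assignment and acts on it. Envelopes drawn at random from a pool have no prescribed order. If one is opened, put aside and replaced by another, no sequence is broken and no required record is missing. Whether the allocation stays random then depends on the conduct of each draw, which concealment procedures are meant to make unnecessary.

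This trial gives a reason to care. Section 2.1 describes lidocaine as very painful on injection, and section 2.2 hypothesises that it adds needless pain. An investigator who shares that view may wish to spare a patient who looks anxious or sore. The outcome is the patient's own pain rating at 1 and 10 minutes, which may well vary with features visible at the examination. Section 9.1 rules out stratification, so comparability of the arms rests on the draw. Section 9.2 compares pain scores by t-test or Wilcoxon test without adjusting for baseline.

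**Working it through.** **Whether the text permits a second draw**

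1. Drawer: the unblinded study investigator (7.2.1).
2. Injector: the study investigator (7.2.1), unblinded (7.1). It is the same role.
3. Order of use: at random from the stock, so there is no next envelope to depart from.
4. Link between envelope and patient before opening: none stated in 7.2.1 or 7.4.3.
5. Reconciliation: none stated anywhere.

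Steps 3 to 5 together mean that a re-draw after opening contradicts nothing in the plan except the word for a random draw.

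**The plan's own figure**

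Inputs from section 9.1: difference 5 mm, SD 10 mm, 64 per arm, 15% dropout, total 221. From section 9.2: two-sided 0.05. Power is not stated; I assume 80%.

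- n per arm = 2 × (1.960 + 0.842)² × 10² / 5² = 62.8, so 63. The t-test version gives 63.8, so 64, as stated.
- Total = 3 × 64 × 1.15 = 220.8, so 221, as stated.
- Standard error of a pairwise difference = 10 × √(2/64) = 1.77 mm.

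**Illustration of scale (assumptions, not data)**

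Half the patients belong to a recognisable subgroup scoring D = 10 mm higher. When such a patient draws one disliked arm, the investigator re-draws once in a share r of cases. Each draw is treated as a fresh one-in-three chance, and 64 per arm is held fixed.

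- Chance that a subgroup patient ends in the disliked arm: a = (1 − r)/3 + r/9.
- Chance of each other arm: o = (1 − a)/2.
- Subgroup share of the disliked arm: a/(a + 1/3). Subgroup share of each other arm: o/(o + 1/3).
- Bias = D × (difference between these shares).
- Type I error = 1 − Φ(1.96 − bias/1.77) + Φ(−1.96 − bias/1.77).

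| r | a | o | Share, disliked arm | Share, other arm | Bias (mm) | Type I error |
|---|---|---|---|---|---|---|
| 10% | 0.311 | 0.344 | 0.483 | 0.508 | 0.25 | 5.2% |
| 30% | 0.267 | 0.367 | 0.444 | 0.524 | 0.79 | 7.3% |
| 50% | 0.222 | 0.389 | 0.400 | 0.538 | 1.38 | 12.3% |

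With D = 5 mm the biases halve to 0.13, 0.40 and 0.69 mm, and the error rates are 5.1%, 5.6% and 6.8%.

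**Direction**

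Steering pain-prone patients away from lidocaine lowers that arm's mean, so it works against the study hypothesis. If lidocaine truly adds 5 mm, power is Φ((5 − bias)/1.77 − 1.96). With D = 10 mm this falls from 81% with no bias to 77%, 66% and 53% at r = 10%, 30% and 50%.

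**The case against.** The strongest reply is that the protocol already deals with the classic failure of concealment. The envelopes are sealed, consent comes first, and a draw from a mixed pool is hard to predict. A reader might infer that the investigator knows the content when choosing an envelope, or enrols patients with the allocation in view. The documents do not support that. Content is known only after opening. Section 4.1 has investigators identify patients, but under section 4.3 eligible patients are invited to "participate in the research study by a member of the research team", and that person need not be the injector. This part of the reply stands. What remains is a re-draw after opening, or tampering.

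A second reply is that the protocol is silent rather than permissive, and that a re-draw might leave traces: a broken seal, a shortfall in the count, or an imbalance in the pre-injection VAS, which a blinded patient completes. This stands in part. It would be too strong to say that a re-draw could never be detected. But the plan states no number of envelopes prepared and assigns nobody to inspect or count them. The pre-injection VAS is taken after the draw, and it need not capture whatever feature prompted a re-draw. These traces cannot be relied on.

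A third reply concerns size. A reader might suppose that a tenth of an arm is swapped for patients differing by 20 mm, which would shift the mean by 0.10 × 20 = 2 mm and raise type I error to about 20%. That is hard to reconcile with section 9.1, because 20 mm is two planned SDs. In a normal distribution with SD 10 mm, even the highest tenth of patients average only about 17.5 mm above the mean. I do not rely on that figure.

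**Conclusion.** The point holds as a weakness in a stated procedure. The unblinded injector draws from an unordered pool, and nothing written prevents or reliably reveals a second draw after opening. It is not evidence that allocation was or will be manipulated, and it does not show that allocations can be foreseen at consent.

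The size is unknown. Under the assumptions shown, the shift is about 0.25 to 1.4 mm against a 5 mm target, with type I error of about 5.2% to 12.3%. If the shift runs against the hypothesis, the harm is lost power instead. These figures depend on the assumed subgroup, its 10 mm difference and the re-draw rate, none of which is in the documents. The conclusion that no safeguard is written also depends on there being no separate site procedure for randomization; the protocol cites none. The change is worth making because it is cheap and the planned analysis would not remove the bias.

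**What to change.** Revise sections 7.2.1 and 7.4.3 as follows:

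- Public Health Sciences, already named in section 9.1, generates the random list in advance and prepares opaque, sealed, sequentially numbered envelopes.
- Envelopes are used strictly in numerical order.
- The study number, date and time are written on the envelope before it is opened.
- All used and unused envelopes are reconciled against the list at the end.

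If the list is blocked, use large or varied block sizes and do not disclose them, because the injector sees every assignment and could otherwise anticipate the end of a block.

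The cost is about 222 numbered envelopes (the enrolment in section 16.0) and a short log, with slightly more paperwork per patient and some added predictability if blocks are used. Sample size, visits and treatments do not change. The same unblinded investigator may still open the envelopes, so the change does not make a re-draw impossible; it makes one break a written order and leave a record.
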